6.3.2 Stratification

Intervention randomization will be stratified according to the following factors:

Part 1

1. Time from symptom onset prior to the day of randomization (≤ 5 days, >5 days)
2. At increased risk of severe illness from COVID-19 (Appendix 10) (yes, no)

Based on the viral kinetics of SARS-CoV-2 and the mechanism of action of MK-4482, treatment with antiviral therapy is likely to have a greater benefit with earlier treatment (≤ 5 days) rather than later treatment (>5 days). In addition, certain characteristics or underlying medical conditions (Appendix 10) have been identified that place patients at increased risk for severe illness from COVID-19, which may result in hospitalization, ICU-level care, ventilatory support, or death. The selection of these criteria as stratification factors will help ensure that the treatment groups will be well balanced within each stratum and the study results will not be confounded by factors suspected to have a potential impact on a participant's response to study intervention.

Of note, at least 75% of participants overall must have at least 1 characteristic or underlying medical condition associated with being at increased risk for severe illness from COVID-19 as defined in Appendix 10. In addition, enrollment of participants with moderate COVID-19 (Appendix 9) will be limited to 50% of total planned sample size.

Part 2

1. Time from symptom onset prior to the day of randomization (≤ 3 days, >3 days)

Based on updates to inclusion criterion #2 wherein the initial onset of signs/symptoms attributable to COVID-19 was amended to ≤ 5 days prior to the day of randomization to target participants earlier in their COVID-19 disease course, the time from symptom onset prior to the day of randomization stratification factor was amended to ≤ 3 days or >3 days. Based on the viral kinetics of SARS-CoV-2 and the mechanism of action of MK-4482, treatment with antiviral therapy is likely to have a greater benefit with earlier treatment (≤ 3 days) rather than later treatment (>3 days).

Of note, all participants must have at least 1 characteristic or underlying medical condition associated with being at increased risk for severe illness from COVID-19 as defined in

Appendix 10. Age is a risk factor independent of other health conditions, so while there is no minimal enrollment for participants >60 years of age, every effort should be made to maximize enrollment of this age group.

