9.6.1 Statistical Methods for Efficacy Analyses

For the evaluation of the primary hypothesis, superiority of MK-4482 compared to placebo with respect to the percentage of participants with either hospitalization or death by Day 29 will be assessed using the stratified Miettinen and Nurminen method [Miettinen, O. 1985]. Superiority will be concluded based on p-value boundaries as described in Section 9.7. Stratification factors include the stratification factors specified in Section 6.3.2. Geographic region will not be used as a stratification factor in the primary analyses, but it may be considered as an additional stratification factor of the stratified Miettinen and Nurminen method for sensitivity analysis if it does not cause sparse data issues. The number of regions along with the specific countries contained within each region will be described in the sSAP. Every effort will be made to ascertain hospitalization and survival status for all participants. For the primary analysis of this endpoint in the MITT population, unknown Day 29 survival status will be treated as failure, and early withdrawal from the study with known Day 29 survival status as alive but unknown Day 29 hospitalization status will not be treated as failure. A sensitivity analysis treating both unknown Day 29 survival status and early withdrawal from the study with known Day 29 survival status as alive but unknown Day 29 hospitalization status as failure will also be provided.

A sensitivity analysis for the primary endpoint will be conducted that includes only COVID-19 related hospitalizations or death by Day 29 in the MITT population. This treatment comparison will be assessed using the stratified Miettinen and Nurminen method as described above. An additional sensitivity analysis excluding hospitalizations that occur early in the course of the study (ie, within a certain time from randomization) will also be performed. Details will be specified in the sSAP.

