9.9 Sample Size and Power Calculations

9.9.1 Sample Size and Power Calculations for Efficacy Analyses (Part 2)

The primary analysis of the Phase 3 study endpoint will include ~1550 participants from Part 2 of the study (~775 for the MK-4482 800 mg group and ~775 for the placebo group) who meet the criteria for inclusion in the MITT population. The primary endpoint is a composite of hospitalization or death. The study has overall power of 97% to demonstrate the superiority of MK-4482 800 mg over placebo at an overall one-sided, 2.5% alpha level, if the underlying treatment difference (MK-4482 minus placebo) in the percentage of participants who are hospitalized and/or die through Day 29 is -6 percentage points.

The power and sample size are based on the following assumptions: 1) an underlying percentage hospitalized/dying of 12% for placebo and 6% for MK-4482 (50% reduction in the relative risk) and 2) a futility/efficacy interim analysis at 50% information as outlined in Section 9.7. The calculation was computed using EAST. To meet the statistical criterion for success (one-sided $p \leq 0.019$ at the final analysis), the observed treatment difference must be approximately -3.0 percentage points or lower, assuming a percentage of 12% for placebo. The observed percentages from Part 1 of this study in the full MITT cohort were 5.4% in the placebo group and 4.1% in the 800 mg group, a difference of only 1.3 percentage points. However, higher percentages of placebo participants met this endpoint within various subgroups of the full study population: 21.4% in the subgroup of participants >60 years of age, 8.0% in the subgroup of participants with TSSO ≤ 5 days and 11.8% in the subgroup of participants with TSSO ≤ 5 days and who were at increased risk for severe illness. In these subgroups, the percentages of participants in the 800 mg group were 5.0% (difference of 16.4 percentage points), 2.1% (difference of 5.9 percentage points) and 3.2% (difference of 8.6 percentage points), respectively. In each of these subgroups, the observed reduction in the relative risk of hospitalization/death associated with 800 mg exceeded 70%. Given the modification to the study population for Part 2, the assumption of 12% for placebo and a 50% reduction in the relative risk are reasonable.

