9.10 Subgroup Analyses

To determine whether the treatment effect is consistent across various subgroups, the estimate of the between-group treatment effect (with a nominal 95% CI) for the primary endpoint will be estimated and plotted within each category of each subgroup. The following are examples of classification variables:

- Age category (≤ 60 vs > 60 years)
- Sex (female, male)
- Baseline (Day 1) disease severity (mild, moderate) per Appendix 9
- Race (American Indian or Alaska Native, Asian, Black or African American, Native Hawaiian or Other Pacific Islander, White)
- Time from symptom onset prior to the day of randomization (≤ 5 days, > 5 days) [Part 1 only]
- Time from symptom onset prior to the day of randomization (≤ 3 days, > 3 days) [Part 2 only]
- At increased risk for severe illness from COVID-19 (yes, no) (Appendix 10) [Part 1 only]
- Geographic region (North America, Europe, Asia Pacific, Latin America)
- Baseline (Day 1) SARS-CoV-2 quantitative assay VL status (undetectable [< 500 copies/mL], low VL [500 to $\leq 10^6$ copies/mL], high VL [$> 10^6$ copies/mL]) [Part 2 only]

- Baseline (Day 1) SARS-CoV-2 qualitative assay VL status (undetectable, detectable) [Part 2 only]
- Baseline (Day 1) SARS-CoV-2 antibody status (negative, positive) [Part 2 only]

Additional subgroups may be defined in the sSAP. Categories of the above subgroups with small sample sizes (<25 per treatment group) may be combined – further detail will be provided in the sSAP.

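### Adding age (≤60, >60) to the Part 2 primary stratified analysis would be a small, low-cost gain in precision; the plan adjusts only for time since symptom onset

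*Combined protocol and SAP*

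**What the plan says.** Section 9.6.1 states that superiority on hospitalization or death by Day 29 "will be assessed using the stratified Miettinen and Nurminen method", and that "Stratification factors include the stratification factors specified in Section 6.3.2". Section 6.3.2 lists a single factor for Part 2: "Time from symptom onset prior to the day of randomization (≤ 3 days, >3 days". Section 9.6.1 mentions one possible extra factor, geographic region, and only for a sensitivity analysis.

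Section 6.3.2 also says "Age is a risk factor independent of other health conditions", but age is neither a randomization factor nor an analysis factor. It enters the efficacy analysis as a subgroup in Section 9.10: "Age category (≤ 60 vs > 60 years".

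Section 9.9.1 gives the Part 1 event rates. Overall they were "5.4% in the placebo group and 4.1% in the 800 mg group". For older participants the placebo rate was "21.4% in the subgroup of participants >60 years of age", and it continues that in the subgroups "the percentages of participants in the 800 mg group were 5.0% (difference of 16.4 percentage points".

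**The concern.** A baseline variable that predicts the outcome, if left out of the strata, leaves its between-group variance in the standard error of the risk difference. It also leaves any chance difference in age mix between the arms in the estimate. A subgroup display does neither job for the primary test. The plan gives its own reason to expect age to be prognostic, age is already recorded for everyone, and the chosen method can take another stratum. What is at stake is some precision in the primary comparison. This matters mainly if the true effect is smaller than the assumed 6 points, because power at the design assumption is already very high.

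**Working it through.** **1. Reproduce the plan's design.** Inputs from Sections 9.7, 9.8 and 9.9.1: 775 per arm, 12% vs 6%, one-sided 0.025, gamma spending with γ = -1, one look at 50% information. This gives an interim boundary of 0.0094 (stated 0.009) and a final boundary of 0.0194 (stated 0.019). The critical differences are -0.048 and -0.030, as stated, and the interim crossing probability under the alternative is 72%, as stated. Overall power is 98.2% without the futility rule and 97.8% with it (stated 97%). The design reproduces.

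**2. The Part 1 age evidence.** Counts are not given; these are inferred from the percentages. Placebo: 21.4% fits 3/14 and 5.4% fits 4/74, leaving 1/60 in those ≤60. The exact 95% interval for 3/14 is 4.7% to 50.8%. At 800 mg: 5.0% fits 1/20 and 4.1% fits 3/73, leaving 2/53 (3.8%). So the gradient is steep in placebo and nearly absent at 800 mg (5.0% vs 3.8%, Fisher p = 1.0).

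**3. Gain from an age stratum.** Assumptions: share *s* of participants >60 is 20% or 30% (the plan does not give it), the placebo rate in those >60 is 21.4%, and the relative effect is the same in both age groups. Onset is left out of both sides because no rates by ≤3 vs >3 days are reported.

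- Placebo rate in those ≤60: q = (p0 - 0.214s)/(1 - s). Treated rates are the placebo rates times p1/p0.
- Unstratified variance: Vu = p0(1 - p0) + p1(1 - p1).
- Stratified variance Vs: the same sum within each age group, weighted by s and 1 - s.
- r = Vs/Vu. Information gain = 1/r - 1. Equivalent participants = 1550(1/r - 1).
- Power at the final boundary = Φ(d/√(r·Vu/775) - 2.075), where d = p0 - p1 and 2.075 is the normal quantile for 0.019. Setting r = 1 gives the unstratified power.

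Worked case, 12% vs 6%, s = 20%: q = (0.12 - 0.0428)/0.8 = 0.0965. Vu = 0.1056 + 0.0564 = 0.1620. Vs = 0.2(0.1682 + 0.0956) + 0.8(0.0872 + 0.0459) = 0.1592. r = 0.983, so information rises 1.7%, or 27 participants.

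| Placebo vs MK-4482 | Information gain (s = 20%, 30%) | Participants | Power without age | Power with age | Gain, points |
|---|---|---|---|---|---|
| 12% vs 6% | 1.7%, 3.0% | 27, 47 | 98.1% | 98.3%, 98.4% | 0.2, 0.3 |
| 12% vs 7% | 1.8%, 3.1% | 27, 47 | 90.2% | 90.7%, 91.1% | 0.5, 0.9 |
| 12% vs 8% | 1.8%, 3.1% | 28, 49 | 71.1% | 71.9%, 72.5% | 0.8, 1.4 |
| 8% vs 4% | 5.3%, 9.4% | 82, 146 | 89.5% | 91.0%, 92.0% | 1.5, 2.5 |

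The 12% vs 7% and 8% vs 4% rows are in Table 8; 12% vs 8% is not, and is shown as a weaker effect. The last row is the most strained: with s = 30%, q is only (0.08 - 0.0642)/0.7 = 2.3%, an age ratio above 9.

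**4. Check on overall power.** Putting r into the two-look calculation with futility, at 12% vs 6% and s from 15% to 50%, gives gains of about 0.1 to 0.6 points. Using the Part 1 rate of 5.0% for treated participants >60, with s from 19% to 50%, gives 0.1 to 0.5.

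**5. Chance imbalance.** The standard deviation of the between-arm difference in share >60 is √(2s(1 - s)/775). Two standard deviations is 4.1 percentage points at s = 20% and 4.7 at 30%. At 12% vs 6% the age gap in event rate, averaged over arms, is (0.1175 + 0.0588)/2 = 0.088 and (0.1343 + 0.0671)/2 = 0.101 respectively. The crude difference would move by 0.041 × 0.088, about 0.4 points, or 0.047 × 0.101, about 0.5 points, against a success threshold near -3.0 points.

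**The case against.** Analysing by the randomization factors is conventional and coherent. The test without age is valid: its standard error already allows for chance imbalance. Age is a planned subgroup, and baseline comparability is tabulated under Section 9.6.3. All of this stands. It limits the point to efficiency, not validity.

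Three stronger readings are tempting, and the documents do not support them.

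- *Age is the strongest predictor in Part 1.* Section 9.9.1 reports only three subgroups and none for obesity or diabetes. Section 4.3.3 lists obesity in 8 of the 11 hospitalized participants, against 5 aged >60 and 5 with diabetes. Without prevalences, strength cannot be ranked.
- *Omitting age costs substantial power.* That needs an age rate ratio near 6. At a 12% placebo rate, a ratio of 6 implies placebo rates in those >60 of 6 × 0.12/(1 + 5s), which is 36% at s = 20% and 29% at s = 30%. Holding the reported 21.4%, the ratio is 2.2 to 2.7. The raw Part 1 contrast should also be expected to weaken. Part 1 allowed up to 25% of participants with no risk factor, all of them necessarily ≤60, whereas in Part 2 everyone ≤60 must have another Appendix 10 condition.
- *Amendment 04 left age uncontrolled by removing the target of about 50% aged >60.* That target set how many older people enrol, not balance between arms, which randomization provides. The stated rationale is that events were occurring across risk factors.

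**Conclusion.** The Part 2 primary test adjusts for time since onset only and leaves out a prognostic factor that the plan itself names. Adding age would be a cheap improvement. It gives about 2-3% more information at a 12% placebo rate, under half a power point at the design assumption, and about 0.5 to 2.5 points in the weaker scenarios checked. It lowered power in none of them.

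These sizes rest on an assumed 20-30% share aged >60, a 21.4% placebo rate in that group that itself rests on about 3 inferred events, a common relative effect, and onset left out of both sides. The gain over the onset-stratified test actually planned was therefore not measured directly. If age is less prognostic in Part 2 than assumed, the gain shrinks towards zero. The planned test is not invalid and the trial is not underpowered on this account.

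**What to change.** Before any Part 2 unblinding, amend Section 9.6.1 so that the primary stratified Miettinen-Nurminen analysis uses four strata: onset (≤3, >3 days) by age (≤60, >60 years). State the stratum weights. Fix a numerical threshold below which strata are collapsed, and the order of collapsing, so that the rule cannot depend on the treatment results. Use the same strata at IA3, IA4 and the final analysis. Keep the onset-only analysis as a sensitivity analysis.

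The cost is a protocol amendment, which Section 9 requires for a change to the primary method, and an analysis factor that was not used in randomization. No new data are needed. Sparseness is unlikely at the final analysis: at a 20% share, about 155 participants per arm would be >60, with about 33 placebo events (155 × 0.214) and 17 treated events (155 × 0.107) at the design rates, before the split by onset.

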Note: Relevant data (ie, central laboratory SARS-CoV-2 RNA results, supplemental oxygen use and methods, oxygen saturation, dialysis and vasopressor use, vital status, and investigator assessment of the participant's ability to independently perform daily activities with minimal or no symptoms) to support determination of the WHO 11-point ordinal score will be collected in eCRFs.

Exploratory:

- Percentage of participants who have any acute care visit. Acute care visit is defined as any hospitalization (any amount of time in a hospital or similar acute care facility, including emergency rooms or facilities created to address hospitalization needs during the COVID-19 pandemic) or emergency room visit or any other acute care visit (including an urgent care visit or visit with any healthcare provider for acute care needs) from randomization through Day 29
- Percentage of participants who have any COVID-19-related acute care visit. Acute care visit is defined as any hospitalization (any amount of time in a hospital or similar acute care facility, including emergency rooms or facilities created to address hospitalization needs during the COVID-19 pandemic) or emergency room visit or any other acute care visit (including an urgent care visit or visit with any healthcare provider for acute care needs) from randomization through Day 29
- Change from baseline in SARS-CoV-2 RNA titer in nasopharyngeal and oropharyngeal swabs separately at various timepoints
- Percentage of participants with undetectable SARS-CoV-2 RNA in nasopharyngeal and oropharyngeal swabs separately at various timepoints

- Viral RNA mutation rate and detection of treatment-emergent sequence variants as assessed by comparison of baseline and post-baseline virus sequencing
- Percentage of participants with undetectable infectious SARS-CoV-2 in nasopharyngeal swabs on Day 3, EOT, Day 10, Day 15, and Day 29.

In addition to the endpoints listed above, survival, supplemental oxygen use, and hospitalization status at the LFU visit (Month 7) will also be summarized.

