9.6 Statistical Methods

This section describes the statistical methods that address the primary and secondary objectives as well as a key exploratory objective for viral RNA endpoints. Methods related to other exploratory objectives will be described in the sSAP. Methods related to PK analysis and PK/PD modeling will be described in a separate modeling and simulation plan authored by QP2. Methods related to dose-response analysis using MCP-MOD will be described in a separate dose-response analyses plan. Methods related to analyses of biomarkers and other exploratory samples will be described separately.

Efficacy results that will be deemed to be statistically significant after consideration of the type I error control for interim analyses are discussed in Section 9.7. There are no adjustments for multiplicity. Statistical testing and inference for safety analyses are described in Section 9.6.2.

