The viral RNA endpoints at earlier time points (Day 3 and EOT) will be important for the dose selection decision from Part 1 of the study. Change from baseline in SARS-CoV-2 RNA titer, calculated as \log_{10} (post) minus \log_{10} (baseline), as measured by quantitative RT-PCR of samples from NP (Parts 1 and 2) and OP (Part 1 only) swabs will be summarized separately by treatment group and time point. The DAO approach will be used to handle missing data for these summary statistics. In addition to summary statistics, treatment differences in change in SARS-CoV-2 RNA titer from baseline over time will be estimated using longitudinal models. Graphical presentations of the change from baseline will be presented and the impact of baseline viral RNA level will be explored using subgroup analyses (defined by level of baseline viral RNA) and analyses/summaries that exclude participants with low baseline levels (eg, viral RNA $<10^6$ copies/mL).

Percentage of participants with undetectable viral RNA (below limit of detection) as measured by qualitative RT-PCR of samples from NP (Parts 1 and 2) and OP (Part 1 only) swabs will be summarized separately by treatment group and time point. Between-treatment differences and 95% CIs will be estimated using the stratified Miettinen and Nurminen method [Miettinen, O. 1985].

WHO 11-point ordinal scale score will be analyzed using the cumulative logits function and the proportional odds model as described by McCullagh [McCullagh, P. 1980]. This methodology provides an estimate of the common odds ratio for assessing differences between treatment groups. In addition to a term for treatment group, the model will include terms for the stratification factors specified Section 6.3.2. The WHO 11-point ordinal scale will be determined based on relevant data collected in eCRFs.

A detailed analysis strategy for key efficacy endpoints is listed in [Table 5](#).

Table 5 Analysis Strategy for Key Efficacy Endpoints

Endpoint/Variable (Description, Time point)	Primary vs. Supportive Approach ^a	Statistical Method ^b	Analysis Population	Missing Data Approach
Primary				
Proportion of participants with either hospitalization or death by Day 29	P	Stratified Miettinen and Nurminen ^c	MITT	As described in 9.6.1
Proportion of participants with either hospitalization or death by Day 29	S	Stratified Miettinen and Nurminen ^c	PP	Observed data only

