Proportion of participants with either COVID-related hospitalization or death by Day 29	S	Stratified Miettinen and Nurminen ^c	MITT	M=F ^d
Proportion of participants with either COVID-related hospitalization or death by Day 29	S	Stratified Miettinen and Nurminen ^c	PP	Observed data only
Time to hospitalization or death by Day 29	S	Stratified log-rank test ^e ; Stratified Cox proportional hazard regression ^f	MITT, PP	Model-based with censoring
Time to COVID- related hospitalization or death by Day 29	S	Stratified log-rank test ^e ; Stratified Cox proportional hazard regression ^f	MITT, PP	Model-based with censoring
Secondary				
Time to sustained resolution or improvement of each targeted self-reported sign/symptoms of COVID-19	P (MITT) S (PP)	Stratified log-rank test ^e ; Stratified Cox proportional hazard regression ^f	MITT PP	Model-based with censoring
Time to progression of each targeted self-reported sign/symptom of COVID-19	P (MITT) S (PP)	Stratified log-rank test ^e ; Stratified Cox proportional hazard regression ^f	MITT PP	Model-based with censoring
Odds of a more favorable response on the WHO 11-point ordinal scale on Day 3, EOT, Day 10, Day 15, and Day 29	P (MITT) S (PP)	Proportional odds model ^g	MITT PP	Model-based
EOT= end of treatment; F= failure; M= missing; MITT= modified intent-to-treat; PP= per-protocol; WHO= World Health Organization.				
^a P=Primary approach; S=Supportive approach.				
^b Statistical models are described in further detail below:				
^c Miettinen and Nurminen method stratified by the factors specified in Section 6.3.2.				
^d M=F is Missing equals to Failure				
^e The stratified log-rank test includes stratification factors specified in Section 6.3.2				
^f Stratified Cox Proportional Hazards regression includes terms for treatment, stratification factors specified in Section 6.3.2				
^g Proportional odds model includes terms for treatment and stratification factors specified in Section 6.3.2.				

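### In Part 2, the comparison of the percentage with undetectable nasopharyngeal viral RNA makes no use of the Day 1 viral RNA level, so its confidence interval, though valid, is probably wider than it needs to be.

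*Combined protocol and SAP*

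**What the plan says.** Section 9.4.1.1 lists the percentage with undetectable RNA as an exploratory endpoint. Section 9.6 nevertheless says that it covers the primary and secondary objectives "as well as a key exploratory objective for viral RNA endpoints", and leaves the other exploratory methods to the supplemental SAP. The method for this endpoint is therefore stated in the plan itself.

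Section 9.6.1 describes the endpoint as "Percentage of participants with undetectable viral RNA (below limit of detection) as measured by qualitative RT-PCR", summarised by swab type, group and time point, and continues: "Between-treatment differences and 95% CIs will be estimated using the stratified Miettinen and Nurminen method". That paragraph names neither strata nor a covariate. Strata for this method are defined in two other places. The primary-endpoint text says "Stratification factors include the stratification factors specified in Section 6.3.2", and a footnote to Table 5 says "Miettinen and Nurminen method stratified by the factors specified in Section 6.3.2". For Part 2, Section 6.3.2 has one factor: "the time from symptom onset prior to the day of randomization stratification factor was amended to" up to 3 days against more than 3 days.

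The Schedule of Activities and Section 8.2.1 put a nasopharyngeal swab on Day 1, before the first dose, for quantitative and qualitative RT-PCR. Baseline RNA is used in two places only:
- In Section 9.6.1, the paragraph on change from baseline in titer has subgroups by baseline level and analyses without low-baseline participants.
- In Section 9.10, "Baseline (Day 1) SARS-CoV-2 quantitative assay VL status" (undetectable, low, high; Part 2 only) is a subgroup variable for the primary clinical endpoint.

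**The concern.** Someone who enters with little or no detectable RNA is more likely to be undetectable at a later visit, whatever the treatment. Section 9.10 foresees an undetectable group at Day 1, and Section 9.6.1 does not remove that group from this percentage. The sponsor treats baseline level as influential for titer, but the comparison of percentages does not draw on it. Variation between participants that a scheduled measurement could explain is then left in the interval. What is at stake is the precision of one of the antiviral comparisons for which the plan promises a between-group interval.

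**Working it through.** **The plan's own figure.** The plan gives no precision or power for this percentage. The nearest virology figure is Table 9, on change in titer. With 60 per group, SD 1.5 and a difference of 1.00: 1.00 / (1.5 × √(2/60)) = 3.65; 3.65 − 1.96 = 1.69; power 95.5% (95.2% with the t distribution), against 95% stated. All nine cells reproduce within 2 points. This neither supports nor weakens the point, because the endpoint differs.

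**Inputs.** 775 per arm (Section 9.9.1). About 80% with baseline RNA of at least 10^6 copies/mL (Section 9.9.2, an expectation for Part 1, assumed here for Part 2). Clearance by baseline level is not in the documents, so it is assumed throughout.

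**Formula.** Let w be the share and p_k the clearance in baseline category k, and p = Σ w·p_k. Stratifying removes the between-category share of the variance, R² = Σ w(p_k − p)² / [p(1 − p)]. The interval shrinks by a factor of about √(1 − R²). With two categories split 20/80, R² = 0.16(p_low − p_high)² / [p(1 − p)]. The half-width before stratifying is 1.96√(2p(1 − p)/775), taking the same rates in both arms.

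| Clearance, low / high baseline | p | R² | Half-width, points | Narrower by |
|---|---|---|---|---|
| 20% / 10% | 0.12 | 0.015 | 3.24 to 3.21 | 0.8% |
| 40% / 20% | 0.24 | 0.035 | 4.25 to 4.18 | 1.8% |
| 80% / 40% | 0.48 | 0.103 | 4.97 to 4.71 | 5.3% |
| 90% / 30% | 0.42 | 0.236 | 4.91 to 4.29 | 12.6% |

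**Three categories (undetectable / low / high), placebo arm.**
- Shares 8/12/80%, clearance 85/50/20%: p = 0.068 + 0.060 + 0.160 = 0.288. Between-category variance is 0.08(0.562)² + 0.12(0.212)² + 0.80(0.088)² = 0.0369, against p(1 − p) = 0.2051. R² = 0.18, about 9% narrower.
- Shares 5/15/80%, clearance 70/40/25%: p = 0.295, R² = 0.0115/0.2080 = 0.055, just under 3% narrower.
- A late visit, shares 8/12/80%, clearance 99/97/90%: p = 0.916, R² = 0.0010/0.0773 = 0.013, about 0.6% narrower.

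Across the wider set of three-category scenarios tried, the variance cut was 5% to 29%. In width that is 1 − √0.95 = 2.5% to 1 − √0.71 = 16%.

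**Gain over the strata already planned.** The figures above compare against no stratification. A simulation used stratified Miettinen-Nurminen intervals that already included one binary factor correlated with viral load, standing in for symptom onset. Baseline log10 RNA was taken as normal with mean 7 and SD 1.2 (about 80% above 10^6), the treatment log odds ratio as 0.5, and the baseline slope as 0 to 1.5 in log odds per log10. At 775 per arm:

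| Baseline effect | Two levels, cut at 10^6 | Four levels |
|---|---|---|
| None | 0.1% wider | 0.2% wider |
| Weak | 1.4% narrower | 1.8% to 2.8% narrower |
| Moderate | 4.2% to 5.8% narrower | 7.3% to 9.5% narrower |
| Strong | 6.5% to 11.2% narrower | 14.3% to 16.0% narrower |

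Coverage was roughly nominal with and without the baseline strata (0.92 to 0.98, within simulation error). Under this distribution almost nobody falls below 500 copies/mL ((2.7 − 7)/1.2 = −3.6 SD). The Section 9.10 categories would therefore behave here like the two-level split. The upper part of the 1% to 16% range needs either a finer split or a real undetectable group with very different clearance.

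**The case against.** The strongest reply is that nothing here is an error. The endpoint is exploratory and its interval is valid. Section 9 also allows exploratory methods to be changed in the supplemental SAP, which is not among the documents. All of that stands, and it limits the point to precision.

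The strata for this endpoint are inferred. Section 9.6.1 does not list them, the sentence that does concerns the primary endpoint, and Table 5 omits this endpoint. The inference is reasonable because no other strata are defined for the method, but it remains an inference.

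The outcome comes from the qualitative assay, while the three Section 9.10 categories come from the quantitative one. They are closely related, not the same measurement. Section 9.10 also lists a qualitative Day 1 variable, but with only two levels. In addition, all participants having a Day 1 value means that it is scheduled; some results will be missing.

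Three stronger readings are tempting, and the documents support none of them:
- A reader might infer that the planned comparison is biased, or could show an antiviral effect that is really a baseline difference. Treatment is randomized, and the planned interval already allows for chance imbalance; the coverage results agree.
- A reader might infer a loss of power. The plan asks only for differences and 95% intervals here, and attaches no test, alpha or power target.
- A reader might extend the point to Part 1. That part has two stratification factors, its enrollment is complete and the dose has been chosen (Section 4.3.3), and the Section 9.10 RNA categories are for Part 2 only. At about 75 per group with a weak relation, the simulated change was only about −0.5% to +1%.

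**Conclusion.** The point holds as a modest gain in precision for one exploratory Part 2 nasopharyngeal endpoint. As the plan most naturally reads, symptom onset is the only stratum and Day 1 RNA plays no part. Using it would probably narrow the interval by about 1% to 16% at 775 per arm. That range depends on assumed relations between baseline RNA and clearance, since the documents give none. The gain is small if the relation is weak, and close to nil at visits where nearly everyone has cleared. The primary test, its alpha and the sample size are unaffected.

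**What to change.** Before Part 2 is unblinded, state in the supplemental SAP that the difference in the percentage with undetectable nasopharyngeal RNA in Part 2 is estimated by Miettinen-Nurminen, stratified by the Section 6.3.2 factor and by the Day 1 quantitative RNA category of Section 9.10 (undetectable, low, high). Put participants without a Day 1 result in their own stratum, and fix in advance the rule for merging sparse strata. The risk difference remains the effect measure.

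The plan already accepts this kind of change: Section 9.6.1 allows region as an extra stratification factor in a sensitivity analysis of the primary endpoint, provided the data do not become sparse. The cost is a sentence or two and one more variable in existing code, with no new data. Two onset levels by four baseline levels give up to eight strata, some of which will need merging. If baseline RNA proves not to be prognostic, the interval widens by only about 0.1% to 0.2%.
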